5.2 Variables

Refer to **Annex 2: Variable definitions** for the definitions of all variables.

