5.2.1.5 Costs associated with HAE attacks

Costs will be estimated for HAE attack episodes, by severity and by treatment location (ED only vs inpatient for severe attacks and home versus office for non-sever attacks). Attack costs will be estimated by summing costs across the medical services utilized during an attack, excluding the costs of on-demand therapies, which are included in the cost-effectiveness model separately. Specific outputs will include:

- Outpatient care
 - Cost per attack treated with a home visit for on-demand treatment administration
 - Cost per attack treated with an office visit for on-demand treatment administration
- Cost per attack treated as ED visit
- Cost per attack treated as inpatient hospitalization

If sample size allows, cost analysis will be restricted to most recent years (2017 – 2020) in order to estimate the most timely and relevant costs. This will be a subgroup analysis of the prophylaxis initiation cohort.

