5.2.1.6 Costs during baseline

Costs will be estimated during a six-month baseline period prior to prophylaxis initiation. Costs will be reported by place of service and by HAE-related health care utilization (minus HAE drug costs) and all-cause utilization. Specific outputs will include:

- Outpatient care
 - Mean total cost of home visits
 - Mean total cost of physician office visits
- Mean total cost of ED visits
- Mean total cost of inpatient hospitalizations

If sample size allows, cost analysis will be restricted to most recent years (2017 – 2020) in order to estimate the most timely and relevant costs. This will be a subgroup analysis of the prophylaxis initiation cohort.

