Annex 2: Variable definitions and code lists

Treatment - Brand Name (Generic)	J Codes and NDCs	Source
Takhzyro (lanadelumab)	J0593 Injection, lanadelumab-flyo, 1 mg (code may be used for Medicare when drug administered under direct supervision of a physician, not for use when drug is self-administered) NDCs: 47783-0644-01	Clinical Pharmacology Database²⁰ and HCPCS²¹
Haegarda (C1 Inhibitor)	J0599 - Injection, HAEGARDA, 10 units (effective Jan 1, 2019) NDCs: 63833-0828-02 63833-0829-02	Clinical Pharmacology Database²⁰ and HCPCS²¹
Cinryze (C1 Inhibitor)	J0598 - Injection, C1 esterase inhibitor (human), 10 units NDCs: 42227-0081-01 42227-0081-05	Clinical Pharmacology Database²⁰ and HCPCS²¹
Ruconest (C1 Esterase Inhibitor, Recombinant)	J0596 - Ruconest, 10 units NDCs: 68012-0350-01 68012-0350-02 71274-0350-01 71274-0350-02	Clinical Pharmacology Database²⁰ and HCPCS²¹
Kalbitor (ecallantide)	J1290 - Injection, ecallantide, 1 mg NDCs: 47783-0101-01	Clinical Pharmacology Database²⁰ and HCPCS²¹
Berinert (C1 Inhibitor)	J0597 - Injection, C1 Esterase Inhibitor (Human), BERINERT, 10 units NDCs: 63833-0825-02	Clinical Pharmacology Database²⁰ and HCPCS²¹
Firazyr (icatibant)	J1744 - Injection, icatibant, 1 mg NDCs: 00093-3066-19	Clinical Pharmacology Database²⁰

	00093-3066-34 00093-3066-93 24201-0207-01 24201-0207-03 54092-0135-01 54092-0135-02 54092-0702-02 54092-0702-03 60505-6214-01 63323-0574-01 63323-0574-86 63323-0574-93 69097-0664-34 69097-0664-68	and HCPCS²¹
Orladeyo (berotralstat)	Newly approved drug (December 2020) and not available in the analysis data set which runs through March 31st 2020.	
Danazol (Danocrine)	NDCs: 00527-1368-01 00527-1369-01 00527-1369-06 00527-1392-01 00555-0633-02 00555-0634-02 00555-0635-02 00555-0635-09 42291-0243-01	Clinical Pharmacology Database²⁰
Cykokapron Lysteda (Tranexamic Acid)	NDCs: 00591-3720-30 55566-2100-01 55566-2110-02 60505-3638-01 60505-3638-03 66993-0090-30 66993-0121-30 69918-0301-30	Clinical Pharmacology Database²⁰
Amicar (Aminocaproic Acid)	NDCs: 17478-0447-08 17478-0768-30 17478-0769-30 49411-0050-30 49411-0051-30 49411-0052-08	Clinical Pharmacology Database²⁰

	52817-0815-08 60219-1637-03 60687-0505-25 62559-0225-30 66689-0330-08 69238-1596-08 69680-0115-30 69680-0116-30 72205-0049-30	
Oxandrin (Oxandrolone)	NDCs: 49884-0301-01 00185-0271-01 49884-0302-02 00185-0272-60	Clinical Pharmacology Database²⁰

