cricothyrotomy/ tracheotomy	emergency tracheotomy (31603) and an emergency cricothyrotomy (31605)	
Dillon 2013²⁵
 
Esposito²⁶

intubation	The appearance of any of the following encounters CPT - 31500 ICD10 - 09HN7BZ, 0DH57BZ, 0DH58BZ, 0WHQ73Z, 0WHQ7YZ, 09HN8BZ, 0B21XEZ, 0BH13EZ, 0BH17EZ, 0BH18EZ, 0CHY7BZ, 0CHY8BZ ICD9 - 96.04, 96.7x, 96, 96.0,96.5	Pandya 2019²⁷ Singh 2020²⁸ De novo code look up
artificial respiration	The appearance of any of the following encounters Invasive mechanical ventilation: CPT - 94002, 94003, 94004, 94005, E0472, K0534 ICD10 - 5A1935Z, 5A1945Z, 5A1955Z noninvasive ventilation: CPT - 94660, A7027, A7034, A7044, E0452, E0470, E0471, E0601, K0183, K0193, K0194, K0532, K0533 ICD10 - 5A09459, 5A09557, 5A09357, 5A09358, 5A09359, 5A0935B, 5A09457, 5A09458, 5A0945B, 5A09558, 5A09559, 5A0955B ICD9 - 93.90 ventilation NOS: CPT- 94656, 94657 ICD10 - 5A0920Z, 5A0945Z, 5A0955Z, 5A19054, 5A0935Z, 5A09358, 5A0935B,	Pandya 2019²⁷ Singh 2020²⁸ Rosenthal 2020²⁹ De novo code look up
Costs	Algorithm and code lists	Source
Home nurse treatment	Standard cost amount for medical service claims with an on-demand drug administration where the place of service is ‘home’	
Physician office visit	Standard cost amount for medical service claims with an on-demand drug administration where the place of service is ‘office’	
ED visit	Standard cost amount for medical service claims where the type of service is coded as ‘emergency room, professional or facility’	
Hospitalization	Standard cost amount for medical service claims where the type of service is coded as ‘acute inpatient facility’	

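### Annex 2's cost rows do not carry out section 5.2.1.5: home and office costs could include the on-demand drug or fall to about zero, and inpatient professional services are left out

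*Protocol*

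**What the plan says.** Section 5.2.1.5 builds the cost of an attack by adding up the medical services used in it, "excluding the costs of on-demand therapies, which are included in the cost-effectiveness model separately". Section 5.2.1.6 applies the same idea to baseline costs, which are to be reported by "HAE-related health care utilization (minus HAE drug costs) and all-cause utilization". Section 5.2 then refers the reader to Annex 2 "for the definitions of all variables".

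The four cost rows in Annex 2 read as follows:

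- **Home nurse and physician office:** "Standard cost amount for medical service claims with an on-demand drug administration where the place of service is" home in the first row and office in the second.
- **ED visit:** standard cost of medical claims whose type of service is "emergency room, professional or facility".
- **Hospitalization:** standard cost of medical claims whose type of service is "acute inpatient facility".

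None of the four rows mentions removing drug cost. Annex 2 also lists the codes by which the on-demand drugs appear on medical claims, for example "J1290 - Injection, ecallantide, 1 mg".

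**The concern.** The home and office rows select claims because they carry the on-demand drug, and then take the standard cost of those claims. Section 5.4.1.2 describes standard cost as approximating the allowed amount for the whole service. The drug is recognised on a medical claim by a J code billed in drug units, so the amount picked up can include the very item that section 5.2.1.5 keeps out.

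The hospitalization row has a different fault. It names facility claims only, although section 5.2.1.5 sums all medical services in the attack and the neighbouring ED row counts professional claims as well.

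Costs of acute attacks are one of the questions under the primary objective. Section 3 says the results, together with literature, will supply updated inputs to the cost-effectiveness model. A drug cost left inside the home or office figure could be added again by the model. An inpatient figure without professional services would not be on the same footing as the ED figure.

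**Working it through.** The protocol states no calculation on this point, so the check compares the text and then illustrates the size.

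**Home and office rows against section 5.2.1.5.** There are two ways to program the Annex 2 wording:

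1. *A claim means the whole visit.* The drug line is inside it. Annex 2 contains no step that takes it out, so drug cost stays in unless the programmer carries the rule over from section 5.2.1.5.
2. *A claim means the drug-coded line.* Applying the exclusion removes that line. Annex 2 names no administration or visit lines to be costed in its place, so the result can be about $0.

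The variable is therefore not fixed, and the error can run in either direction.

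**ED and hospitalization rows.** Both select by type of service, not by presence of the drug. The ED row has no drug exclusion either, so on-demand drug lines on ED claims could remain. For the hospitalization row the drug argument does not carry over: section 5.3.1.2 says the data source does not record drugs used during hospital stays. What remains there is the facility-only wording.

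**Illustration of size, home and office.** Inputs from Annex 3, Table 2 (prior base case): home nurse $179, office visit $266; non-severe attacks treated by self 64.9%, home nurse 13.8%, outpatient 21.3%. These shares sum to 100.0%. Here outpatient is costed at the office figure. Let D be the drug cost left in the claim; the protocol gives no value, so D is assumed.

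- Share affected: 13.8% + 21.3% = 35.1%.
- Mean service cost per non-severe attack with the drug excluded: 0.138 × 179 + 0.213 × 266 = 24.70 + 56.66 = $81.36.
- With the drug left in: 81.36 + 0.351 × D.

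| Assumed D | Home | Office | Mean per non-severe attack |
|---|---|---|---|
| $0 | $179 | $266 | $81.36 |
| $500 | $679 | $766 | $256.86 |
| $1,000 | $1,179 | $1,266 | $432.36 |
| $5,000 | $5,179 | $5,266 | $1,836.36 |
| $10,000 | $10,179 | $10,266 | $3,591.36 |

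Each $1,000 left in adds 0.351 × 1,000 = $351. In the other direction, if the drug line is the only one selected and is then removed, the $81.36 goes to about $0.

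The same error can be set against drug plus service cost, assuming the model charges D once to every non-severe attack:

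- D = $1,000: (1,081.36 + 351) / 1,081.36 = 1.32.
- D = $10,000: (10,081.36 + 3,510) / 10,081.36 = 1.35.

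**Illustration of size, inpatient.** If professional services equal a fraction p of the facility amount, leaving them out understates the cost by p / (1 + p). For an assumed p of 10% to 25% this is 0.10/1.10 = 9% to 0.25/1.25 = 20%. The protocol gives no p.

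**The case against.** The strongest reply is that the exclusion is stated in section 5.2.1.5, with its reason, and again for HAE-related costs in section 5.2.1.6. Annex 2 is silent on it and does not reverse it. A reader might infer that the drug will be counted twice; the documents do not support that, since it would require a programmer to disregard both sections. This stands, and the point is accordingly about what could happen. It does not make the rows adequate, because applying the exclusion to them as worded may leave nothing to cost.

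A second reply is that line-level filters belong in a programming specification or an analysis plan, which is not shown. That is fair for the mechanics. But Annex 2 is the protocol's own definition, and what it states does not match section 5.2.1.5.

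Third, the size is assumed. A reader might infer from the table that home cost would rise about 57-fold (10,179 / 179 at D = $10,000). That ratio depends on an unsupported price and divides by a small component; against drug plus service cost the same error is about 1.3-fold. Table 2 also prints the new figure beside $179 and $266, so a gross inflation would probably be noticed.

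Fourth, the protocol does not show how the data source groups inpatient professional claims by type of service. A reader might infer that the inpatient input will be 9% to 20% too low; that range rests only on the assumed p. The difference in wording between the ED and hospitalization rows does not depend on it.

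**Conclusion.** The point holds as a mismatch between Annex 2 and section 5.2.1.5, in two parts. The home and office rows are incomplete: applied literally they could include drug cost that the model adds separately, and if only the drug line is selected and then removed they could fall to about zero. The hospitalization row, as worded, omits inpatient professional services that section 5.2.1.5 would sum.

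The documents do not establish that double counting will occur, nor do they fix its size. The one figure that needs no drug price is the rate of $351 per non-severe attack for each $1,000 left in. It rests on the prior treatment mix of 35.1% home nurse or outpatient, which the study itself may revise. The intent to exclude the drug is clear. Because these costs belong to the primary objective and are meant to inform the model, the rows should be corrected before the cost analysis is run.

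**What to change.** Rewrite the Annex 2 cost rows at claim-line level and refer them to section 5.2.1.5:

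- **Home and office:** standard cost of all medical lines of the attack episode at that place of service, minus lines with the listed on-demand drug codes (J0596, J0597, J1290 and J1744, and J0598 where Cinryze is used for an acute attack).
- **ED:** keep professional and facility claims, with the same drug-line exclusion.
- **Hospitalization:** facility plus professional services from admission to discharge.
- **Keep ED and inpatient as separate components.** Add the preceding ED visit only to the per-attack inpatient total in section 5.2.1.5. Do not add it to the per-hospitalization model input unless the model structure calls for it. Table 2 lists ED visit and hospitalization costs separately, so folding one into the other could itself count the ED visit twice.

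The cost is a change of wording, a filter on drug codes and a wider selection of inpatient claims. Compared with a literal run on whole visits, home and office costs would be lower; compared with a run that strips a drug-only line, they would be higher. Inpatient cost would rise by whatever professional services the present wording leaves out.

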Annex 3: Results Table Shells

Table 1: Baseline characteristics of patients with HAE

Characteristic	RWE results	Notes	Prior ICER review base case	Prior ICER review source
Mean age			39.63	Banerji et al. 2017, ³⁰ Longhurst et al. 2017, ³¹ Zuraw et al. 2010 ³²
Female, %			68.4%	Banerji et al. 2017, ³⁰ Longhurst et al. 2017, ³¹ Zuraw et al. 2010 ³²
Mean weight, females			76.4	Fryar et al. 2016 ³³
Mean weight, males			88.8	Fryar et al. 2016 ³³
List of top 10 non-HAE therapies (therapeutic class)				

Table 2: Attack rates, utilization, and costs in the six-month baseline period before initiation of prophylaxis treatment

Characteristic	RWE results	Notes	Prior ICER review base case	Prior ICER review source
ATTACK RATES AND TREATMENTS ADMINISTERED				
Mean attack rate per month (HAE-specific severe and non-severe)			3.39	Banerji et al. 2017, ³⁰ Longhurst et al. 2017, ³¹ Zuraw et al. 2010 ³²
Number of patients who are attack free in baseline period before starting prophylaxis therapy		Due to drug indications and health plan requirements, this is expected to be minimal or 0.	-	

Distribution of severe attack free months			-	
Proportion of attacks, by severity				
Severe - HAE specific			-	
Severe - All-cause			-	
Non-severe			-	
Treatment administered – Non-severe attacks				
Self			64.9%	Riedl et al, 2015 ³⁴
Home nurse			13.8%	Riedl et al, 2015 ³⁴
Outpatient			21.3%	Riedl et al, 2015 ³⁴
% of severe-HAE specific attacks resulting in hospitalization			40.9%	Zilberberg et al 2011a ³⁵
% of hospitalized patients receiving cricothyrotomy/tracheotomy			40.0%	Bork et al ³⁶
% of cricothyrotomy/tracheotomy patients who receive artificial respiration			40.0%	Bork et al ³⁶
% of hospitalized patients who are intubated			60.0%	Bork et al ³⁶
% of intubated who receive artificial respiration			26.7%	Bork et al ³⁶
% of attacks treated with these on-demand drugs				Assumption in model
Berinert			25%	
Kalbitor			25%	

Firazyr			25%	
Ruconest			25%	
BASELINE HAE-SPECIFIC COST OUTCOMES				
Costs per home nurse			\$179	Graham et al 2017 ³⁷
Costs per physician office visit			\$266	Graham et al 2017 ³⁷
Costs per ED visit			\$1,796	Zilberberg et al 2011a and 2011b ^{35,38}
Costs per hospitalization			\$5,782	Zilberberg et al 2011a and 2011b ^{35,38}
BASELINE HAE-SPECIFIC UTILIZATION OUTCOMES				
Average number of home visits			-	
Average number physician office visits			-	
Average number of ED visits			-	
Average number of hospitalizations			-	
Pharmacy – on-demand drug utilization (# of scripts and total dose)			-	

Table 3: Descriptive analysis during follow-up (post initiation of prophylaxis)

Characteristic	Takhzyro initiators	Haegarda initiators	Cinryze initiators*	Notes
Mean age at initiation				
Female, %				

Distribution of severe attack free months				
Mean attack rate per month – severe-HAE specific- follow up period				
Proportion of patients with PDC >80%				
Switching- % patients switching to Takhzyro	N/A			
Switching- % patients switching to Haegarda		N/A		
Switching- % patients switching to Cinryze			N/A	

*Cinryze patients were required to be adherent to therapy in the 90 days post initiation to determine that they were taking Cinryze prophylactically (versus on-demand use). Takhzyro and Haegarda patients were not required to demonstrate adherence in the 90 days post initiation.

Table 4: Exploratory dose reduction outcomes

Characteristic	Takhzyro initiators	Notes
Percent of Takhzyro patients attack free for 6-month period		
Percent patients on every 4-week dosing for 6 months		
Percent of patients that titrated down to every 2-week dosing		

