5.2.1.8 Hospitalization utilization

For those patients with severe attacks, defined by inpatient hospitalization or ED visit, we will calculate the percentage of patients hospitalized. Of those hospitalized, we will also estimate utilization for the following:

- Percent of patients receiving cricothyrotomy/tracheotomy
 - Percent that also receive artificial respiration
- Percent of patients intubated
 - Percent that also receive artificial respiration

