5.4 Statistical analysis

5.4.1.1 Baseline attack rates (primary objective)

Attack rates will be calculated as the total number of attacks in the cohort divided by the number of person-months during baseline (six months prior to initiation of prophylaxis treatment). The rates

and percentages of attacks by severity (severe all-cause, severe-HAE specific, non-severe) will also be calculated for the baseline cohort.

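### Table 2 puts hospitalization per attack and airway procedures per patient, and sections 4 and 5.2.1.8 use a different unit and severe-attack definition for hospitalization

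*Protocol*

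**What the plan says.** Four places in the protocol bear on this.

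- **Section 5.4.1.1** makes the attack rate an event rate: "Attack rates will be calculated as the total number of attacks in the cohort divided by the number of person-months during baseline".
- **Annex 3, Table 2**, which covers the six-month baseline, reports the share "of severe-HAE specific attacks resulting in hospitalization" (prior base case 40.9%). The following rows report the share "of hospitalized patients receiving cricothyrotomy/tracheotomy" (40.0%) and the share "of hospitalized patients who are intubated" (60.0%), each followed by the share of those patients who receive artificial respiration.
- **Section 5.2.1.8** starts from patients with severe attacks, identified by an inpatient stay or an ED visit, and says "we will calculate the percentage of patients hospitalized". It continues: "Of those hospitalized, we will also estimate utilization for the following", listing "Percent of patients receiving cricothyrotomy/tracheotomy" and the share intubated. The primary research question in section 4 is also put per patient for both hospitalization and procedures.
- **Annex 2** defines intubation and artificial respiration by "The appearance of any of the following encounters" followed by code lists. The cricothyrotomy/tracheotomy row lists two procedure codes without that wording.

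Sections 3 and 4 say that the results are meant to update the inputs of the earlier cost-effectiveness model.

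**The concern.** Read downwards, Table 2 looks like a chain: attacks per month, share of severe attacks hospitalized, share of hospitalized cases with an airway procedure. The denominator changes from attacks to patients between the second and third links. A patient with three hospitalized attacks and one intubation adds three to the count of hospitalized attacks, but counts once, as intubated, in the patient share.

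The methods text does not settle the unit, because it puts hospitalization itself per patient. Nor does it settle which severe attacks count. Section 5.2.1.4 sets up an all-cause and an HAE-specific definition; the Table 2 hospitalization row uses the HAE-specific one, and 5.2.1.8 names neither. An analyst following 5.2.1.8 and one following Table 2 would produce different hospitalization shares, and possibly different sets of hospitalized patients below them. At stake is whether the model team gets a procedure probability that can be applied to an attack.

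**Working it through.** The protocol states no figure of its own for procedures per attack, so there is nothing to reproduce. The check has four steps.

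**1. Units side by side**

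| Quantity | Sections 4 and 5.2.1.8 | Annex 3, Table 2 |
|---|---|---|
| Hospitalization share | per patient with severe attacks | per HAE-specific severe attack |
| Severe-attack definition | not limited to HAE-specific in 5.2.1.8 | HAE-specific |
| Cricothyrotomy/tracheotomy and intubation shares | per hospitalized patient | per hospitalized patient |

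The procedure rows agree across the document. The hospitalization share does not.

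**2. Are repeat hospitalized attacks plausible?** The table's prior rate gives 3.39 × 6 = 20.3 attacks per patient over baseline, and section 5.2.1.4 merges only events within five days. The severe share is not given, so 5%, 10% and 20% are assumed. With 40.9% of severe attacks hospitalized, the expected number of hospitalized attacks per patient is m = 20.34 × severe share × 0.409 = 0.42, 0.83 or 1.66. Under a Poisson count, the mean among patients with at least one is m/(1 − e^−m), about 1.2, 1.5 or 2.1.

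**3. Size if the risk is the same at every hospitalized attack.** Let k be hospitalized attacks per hospitalized patient (assumed, since the protocol does not give it), p the procedure probability per hospitalized attack, and P the patient share. With constant, independent risk:

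P = 1 − (1 − p)^k, so p = 1 − (1 − P)^(1/k), and the overstatement is P/p.

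The prior base-case shares serve only to set a level for P:

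| k | Cricothyrotomy/tracheotomy (P = 40.0%): p | P/p | Intubation (P = 60.0%): p | P/p |
|---|---|---|---|---|
| 1 | 40.0% | 1.00 | 60.0% | 1.00 |
| 1.5 | 28.9% | 1.39 | 45.7% | 1.31 |
| 2 | 22.5% | 1.77 | 36.8% | 1.63 |
| 3 | 15.7% | 2.55 | 26.3% | 2.28 |

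At k = 2, for example, p = 1 − √0.60 = 0.2254 and 0.40/0.2254 = 1.77. Multiplied by the 40.9% hospitalization share, cricothyrotomies/tracheotomies per severe attack are 0.409 × 0.40 = 0.164 as labelled and 0.409 × 0.2254 = 0.092 on the attack unit. For intubation they are 0.409 × 0.60 = 0.245 and 0.409 × 0.3675 = 0.150. For small patient shares (2% to 10%) the factor is close to k: 1.99 to 1.95 at k = 2.

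**4. Direction without the constant-risk assumption.** Take ten hospitalized patients: nine with one stay and no procedure, one with four stays.

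- Procedure in one of the four stays: patient share 1/10 = 10%, attack share 1/13 = 7.7%. The patient share overstates.
- Procedure in all four: patient share still 10%, attack share 4/13 = 30.8%. The patient share understates.

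The same patient share fits both, so the attack share cannot be recovered from it, even if the mean number of stays is known.

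**The case against.** The strongest reply is that the methods text is coherent: sections 4 and 5.2.1.8 put hospitalization and procedures per patient, and one Table 2 row is the outlier. That is fair, and it means the contradiction could be resolved in either direction. It does not remove the contradiction, and an all-patient version would still not combine with an attack rate per person-month.

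A second reply is that the protocol never says these rows are multiplied. It says that literature will supplement the results, and it refers to a separate Model Analysis Plan for the use of attack estimates. This stands: the consequence for the model is conditional on that use.

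Some stronger readings are tempting, but the documents do not support them.

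- **That procedures per attack are necessarily overstated.** This needs repeat hospitalized attacks and broadly similar risk at each; the effect is nil at one attack per patient and can reverse.
- **That any code at any time counts for every procedure.** The wording in Annex 2 is attached to intubation and artificial respiration only. Section 5.2.1.8 does restrict all the procedures to hospitalized patients, though it does not tie the code to the attack's stay.
- **That home breathing equipment inflates the artificial respiration rows.** The protocol gives no code titles, and artificial respiration is counted only among patients who already have an airway procedure.
- **That the two procedure rows must be exclusive because the prior values sum to 40.0% + 60.0% = 100%.** Nothing in the protocol says so, and descriptive percentages may overlap.

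**Conclusion.** The concern holds as an inconsistency of unit and of severe-attack definition, with a conditional effect on the model inputs. The inconsistency can be read directly from Table 2, section 4 and section 5.2.1.8. If the shares are combined with the attack rate, the result is assured to be correct only when each hospitalized patient has exactly one hospitalized attack. Under constant risk and an assumed two such attacks per patient, the overstatement is about 1.8-fold for cricothyrotomy/tracheotomy and 1.6-fold for intubation at the prior base-case shares. With clustering in patients with repeat stays it may be an understatement. The actual size cannot be found from the protocol, which gives neither the number of hospitalized attacks per patient nor the way the model uses the shares. The missing link between code and stay is a smaller, separate gap for intubation and artificial respiration.

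**What to change.** Align section 4, section 5.2.1.8 and Table 2 on one unit and one severe-attack definition:

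- Report hospitalization per HAE-specific severe attack.
- Report cricothyrotomy/tracheotomy, intubation and the artificial respiration rows with hospitalized HAE-specific attacks as the unit, so that artificial respiration is a share of the hospitalized attacks with the given procedure.
- State in Annex 2 that a procedure or ventilation code counts only when it is dated within that attack's stay.
- Keep the patient-level percentages as secondary rows, labelled as shares over the six-month baseline.

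The code lists can stay as they are, and the procedure rows need not be made exclusive. The cost is rewording and some extra rows, from the same claims. The drawback is that a procedure billed with a date outside the stay would be missed.
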